### **Duration of response**

DoR (per RECIST 1.1 using Investigator assessment) will be defined as the time from the date of first documented response until the first date of documented progression or death in the absence of disease progression (ie, date of PFS event or censoring – date of first response + 1). The end of response should coincide with the date of progression or death from any cause used for the RECIST 1.1 PFS endpoint.

The time of the initial response will be defined as the latest of the dates contributing toward the first visit response of CR or PR. If a patient does not progress following a response, then their DoR will be censored at the PFS censoring time. DoR will not be defined for those patients who do not have documented response.

### **Proportion of patients alive and progression free at 6 months after randomization (PFS6)**

The PFS6 will be defined as the Kaplan-Meier (KM) estimate of PFS (per RECIST 1.1 as assessed by the Investigator) at 6 months after randomization.

### **Proportion of patients alive at 18 months after randomization (OS18)**

The OS18 will be defined as the KM estimate of OS (per RECIST 1.1 as assessed by the Investigator) at 18 months after randomization.

#### **9.4.1.2 Calculation or derivation of safety variables**

##### **Adverse events**

Data from all cycles of treatment will be combined in the presentation of safety data. AEs (both in terms of Medical Dictionary for Regulatory Activities [MedDRA] preferred term and CTCAE grade) will be listed individually by patient.

Any AE occurring before treatment with IP will be included in the data listings but will not be included in the summary tables of AEs. AEs observed up until 90 days following discontinuation of the immunotherapy agents (ie, the last dose of durvalumab +olaprib or durvalumab + placebo) or until the initiation of the first subsequent therapy following discontinuation of treatment (whichever occurs first) will be used for the reporting of the AE summary tables. Further details will be provided in the SAP. Any AE that occurs after a patient has received further therapy for cancer (following discontinuation of IP) will be flagged in the data listings.

A separate data listing of AEs occurring more than 90 days post-last dose of the latest IP will be produced. These events will not be included in the AE summaries.

##### **Other significant adverse events (OAEs)**

During the evaluation of the AE data, an AstraZeneca medically qualified expert will review the list of AEs that were not reported as SAEs and AEs leading to discontinuation. Based on the expert's judgment, significant AEs of particular clinical importance may, after consultation with the Global Patient Safety Physician, be considered OAEs and reported as such in the CSR. A similar review of laboratory/vital signs/ECG data will be performed for identification of OAEs. Examples of these are marked hematological and other

laboratory abnormalities and certain events that lead to intervention (other than those already classified as serious) or significant additional treatment.

### **Safety assessments**

For the change from baseline summaries for vital signs, laboratory data, and physical examination, the baseline value will be the latest result obtained prior to the start of the IP.

Corrected calcium product will be derived during creation of the reporting database using the following formula:

$$\text{Corrected calcium (mmol/L)} = \text{Total calcium (mmol/L)} + ([40 - \text{Albumin (g/L)}] \times 0.02)$$

The denominator used in laboratory summaries will include only evaluable patients, in other words, those who had sufficient data to have the possibility of an abnormality.

For example:

- If a CTCAE criterion involves a change from baseline, evaluable patients would have both a pre-dose and at least 1 post-dose value recorded.
- If a CTCAE criterion does not consider changes from baseline, to be evaluable, the patient only need to have 1 post-dose value recorded.

The denominator in vital signs data should include only those patients with recorded data.

#### **9.4.1.3 Calculation or derivation of patient-reported outcome variables**

All items/questionnaires will be scored according to published scoring guidelines.

#### **EORTC QLQ-C30**

The EORTC QLQ-C30 consists of 30 questions that can be combined to produce 5 function scales (physical, role, cognitive, emotional, and social), 3 symptom scales (fatigue, pain, and nausea/vomiting), and a global measure of health status. The EORTC QLQ-C30 will be scored according to the EORTC QLQ-C30 scoring manual ([Fayers et al 2001](#)). An outcome variable consisting of a

score from 0 to 100 will be derived for each of the symptom scales, each of the function scales, and the global health status scale in the EORTC QLQ-C30 according to the EORTC QLQ-C30 scoring manual. Higher scores on the global health status and function scales indicate better health status/function, but higher scores on symptom scales represent greater symptom severity.

Definition of clinically meaningful changes

Changes in score compared with baseline will be evaluated. A minimum clinically meaningful change is defined as an absolute change of  $\geq 10$  in the score from baseline for scales from the EORTC QLQ-C30 (Osoba et al 1998). For example, a clinically meaningful improvement in physical function (as assessed by EORTC QLQ-C30) is defined as an increase of  $\geq 10$  in the score from baseline, whereas a clinically meaningful deterioration is defined as a decrease of  $\geq 10$  in the score from baseline. At each post-baseline assessment, the change in symptoms/ functioning from baseline will be categorized as improvement, no change, or deterioration as shown in Table 16. A patient’s best overall response in symptoms, function, or global health status/QoL will be derived as the best response the patient achieved, based on evaluable PRO data collected during the study period. Additional details will be provided in the SAP.

**Table 16 Mean change and visit response in health-related quality of life**

Score	Change from baseline	Visit response
EORTC QLQ-C30 global quality of life score	$\geq +10$ $\geq -10$ Otherwise	Improvement Deterioration No change
EORTC QLQ-C30 symptom scales	$\geq +10$ $\geq -10$ Otherwise	Deterioration Improvement No change
EORTC QLQ-C30 function scales	$\geq +10$ $\geq -10$ Otherwise	Improvement Deterioration No change

EORTC QLQ-C30 European Organisation for Research and Treatment of Cancer 30-item core quality of life questionnaire.

For each subscale, if  $< 50\%$  of the subscale items are missing, then the subscale score will be divided by the number of non-missing items and multiplied by the total number of items on the subscales (Fayers et al 2001). If at least 50% of the items are missing, then

that subscale will be treated as missing. Missing single items are treated as missing. The reason for any missing questionnaire will be identified and recorded. If there is evidence that the missing data are systematic, missing values will be handled to ensure that any possible bias is minimized.

#### Time to symptom deterioration

For each of the symptoms scales in the EORTC QLQ-C30, time to symptom deterioration will be defined as the time from randomization until the date of the first clinically meaningful symptom deterioration (an increase of  $\geq 10$  in the score from baseline) or death (by any cause) in the absence of a clinically meaningful symptom deterioration, regardless of whether the patient discontinues study treatment or receives another anticancer therapy prior to symptom deterioration. Death will be included as an event only if the death occurs within 2 visits of the last PRO assessment where the symptom change could be evaluated.

Patients whose symptoms (as measured by EORTC QLQ-C30) have not shown a clinically meaningful deterioration and who are alive at the time of the analysis will be censored at the time of their last PRO assessment where the symptom could be evaluated. Also, if symptoms deteriorate after 2 or more missed PRO assessment visits or the patient dies after 2 or more missed PRO assessment visits, the patient will be censored at the time of the last PRO assessment where the symptom could be evaluated. If a patient has no evaluable visits or does not have baseline data they will be censored at Day 0. The population for the analysis of time to symptom deterioration will include a subset of the FAS who have baseline scores of  $\leq 90$ .

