**Table 1 Schedule of assessments for patients who are receiving study treatment**

	Screening	C1 a	C2 a	C3 a	C4 a	C5 to PD a,b	EOT visit c	For details, see Section	
Week	-4 to -1	0	q4w ±3 days unless dosing needs to be held for toxicity reasons						
Day	-28 to -1	1	q28days ±3 days unless dosing needs to be held for toxicity reasons						
Pharmacokinetics									
Durvalumab PK sample (serum)		X n	X o		X o			8.5.1.1	
Olaparib PK sample (plasma)		X o	X o		X o			8.5.1.2	
Monitoring									
WHO/ECOG performance status	X	X	X	X	X	X	X	8.2.5	
AE/SAE assessment p	<----->								8.3
Drug accountability		X	All visits						6.3
IP administration									
Durvalumab q		X r	X r	X r	X r	X r		6.1.1.1	
Olaparib/placebo q		X	X	X	X	X		6.1.1.2	
Other assessments and assays									
Tumor biopsy (FFPE sample) s	X s					X s		8.1.2, 8.8.1.1	
Genetic sample	X							8.7, Appendix D	
Durvalumab immunogenicity assessment (ADA sampling to identify ADA responses in patient circulation)		X o	X o		X o			8.5.2	
Whole blood for gene expression (PaxGene-RNA tubes)	X o	X o	X o			X o		8.8.1.2	
Whole blood – exploratory analysis (mandatory) t	X	X	X	X	X	X	X	8.8.1.3	
Urine (mutational analysis)	X	X	X	X	X	X	X	8.8.1.4	
ctDNA (plasma)	X	X	X	X	X	X	X	8.8.1.5	
EORTC QLQ-C30 and EQ-5D-5L u		X	q4w (±7 days relative to Cycle 1 Dose 1 date) until treatment discontinuation						8.1.4.1, 8.1.4.2

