**Table 2 Schedule of assessments for patients who have discontinued all study treatment**

Evaluation	Time since last dose of IP							12 months and every 2 months thereafter (±2 weeks)	For details, see Section
	Day (±3)	Months (±1 week)							
	30	2	3	4	6	8	10		
EORTC QLQ-C30 and EQ-5D-5L i	X	X	X	Patients who enter follow-up without PD and do not attain PD by follow-up Month 3 will continue with q8w (±7 days relative to follow-up Month 3 visit date) until PD and thereafter complete 1 more assessment. Patients who attain PD by follow-up Month 3 will complete only 1 additional q8w assessment.				8.1.4.1, 8.1.4.2	
Tumor assessment (CT or MRI) (RECIST 1.1) j	q8w ±1 week beginning 8 weeks after randomization for the first 48 weeks, and then q12w ±1 week thereafter (relative to the date of randomization) until clinical progression with or without RECIST 1.1-defined radiological progression. An additional follow-up scan is requested, if clinically feasible. The schedule of q8w ±1 week for the first 48 weeks and then q12w ±1 week thereafter MUST be followed regardless of any delays in dosing.							8.1	

- a For women of childbearing potential only. A urine or serum pregnancy test is acceptable.
- b WHO/ECOG performance status should also be collected at other site visits that the patient attends; if appropriate, site staff are available to collect such information. In addition, WHO/ECOG performance status should be provided when information on subsequent anticancer therapy is provided, where possible.
- c Details of any treatment for UC after the last dose of the IP must be recorded in the eCRF. At minimum, collect the start date and description of the subsequent anticancer therapy.
- d Patients may be contacted in the week following data cutoffs to confirm survival status. Details of any treatment for UC after the last dose of the IP must be recorded in the eCRF.
- e Individual sites are required to indicate in the eCRF if a urinalysis was performed during an unscheduled visit.
- f Free T3 or free T4 will only be measured if TSH is abnormal or if there is clinical suspicion of an AE related to the endocrine system.
- g PK and immunogenicity samples for durvalumab are collected 90 days (3 months; ±7 days) after treatment with durvalumab ends. In addition, a final sample for ADA is taken 6 months (±7 days) after treatment with durvalumab ends.

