### **Progression-free survival**

PFS (per RECIST 1.1 as assessed by the site Investigator) will be defined as the time from the date of randomization until the date of objective disease progression or death (by any cause in the absence of progression) regardless of whether the patient withdraws from therapy or receives another anticancer therapy prior to progression (ie, date of event or censoring – date of randomization + 1). Patients who have not progressed or died at the time of analysis will be censored at the time of the latest date of assessment from their last evaluable RECIST 1.1 assessment. However, if the patient progresses or dies after 2 or more consecutive missed visits, the patient will be censored at the time of the latest evaluable RECIST 1.1 assessment prior to the 2 missed visits. If the patient has no evaluable visits or does not have baseline data, they will be censored at Day 1 unless they die within 2 visits of baseline; then they will be treated as an event with date of death as the event date.

The PFS time will always be derived based on scan/assessment dates and not visit dates.

RECIST 1.1 assessments/scans contributing toward a particular visit may be performed on different dates. The following rules will be applied:

- For Investigator assessments, the date of progression will be determined based on the earliest of the RECIST 1.1 assessment/scan dates of the component that indicates progression.

- When censoring a patient for PFS, the patient will be censored at the latest of the scan dates contributing to a particular overall visit assessment.

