#### Time to health-related quality of life/function deterioration

For global health status/QoL, time to deterioration will be defined as the time from the date of randomization until the date of the first clinically meaningful deterioration (a decrease of  $\geq 10$  in the function scales or the global health status/QoL from baseline) or death (by any cause) in the absence of a clinically meaningful deterioration, regardless of whether the patient discontinues study treatment or receives another anticancer therapy prior to global health status/QoL or functional deterioration. Death will be included as an event only if the death occurs within 2 visits of the last PRO assessment where the global health status/QoL or functional change could be evaluated.

Patients whose HRQoL or function (as measured by EORTC QLQ-C30) have not shown a clinically meaningful deterioration and who are alive at the time of the analysis will be censored at the time of their last PRO assessment where the HRQoL/function could be evaluated. Also, if HRQoL/function deteriorates after 2 or more missed PRO assessment visits or the patient dies after 2 or more

missed PRO assessment visits, the patient will be censored at the time of the last PRO assessment where HRQoL/function could be evaluated. If a patient has no evaluable visits or does not have baseline data they will be censored at Day 0. The population for the analysis of time to HRQoL/function deterioration will include a subset of the FAS who have baseline scores of  $\geq 10$ .

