#### **EORTC QLQ-C30**

Time to symptom deterioration in symptom, function, and HRQoL will be analyzed respectively for each of the 3 multiple-item symptom scales (fatigue, pain, and nausea/vomiting), the 5 function scales (physical, role, cognitive, emotional, and social), and global health status/QoL. These analyses will be performed for the FAS using a log-rank test stratified by the same covariates as for the primary PFS endpoint and illustrated using a KM plot by treatment arm. Summaries of the number and percentage of patients who have an event, as well as who were censored, will be provided along with the medians for each treatment.

A summary of the symptom improvement rate for each of the 3 symptom scales will be produced. Similarly, a summary of the best HRQoL/function response rate for each of the 5 function scales and global health status/QoL will be produced. The best symptom response rate and HRQoL/function response rate will be analyzed by comparing the treatment arms using a logistic regression model as described for the analysis of ORR. The odds ratio, p-value, and 95% CI will be presented graphically on a forest plot.

Summaries of absolute and change from baseline values for each of the 3 symptom scales/items, 5 individual symptom items (dyspnea, loss of appetite, insomnia, constipation, and diarrhea), 5 function scales and the global health status/QoL score, and each functional domain will be reported by visit for each treatment arm. The mean change from baseline will be analyzed for each symptom scale and function scale of interest using a mixed model for repeated measures and potentially a piecewise linear model to further support data interpretation. Full details of this and appropriate sensitivity analyses will be described in full in the SAP.

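### The missed-visit censoring rule for PRO time to deterioration does not limit the censoring date to assessments before the gap, so read literally it censors at or after the observed deterioration

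*Protocol*

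**What the plan says.** Protocol section 9.4.1.3, under Time to symptom deterioration, gives the trigger: "if symptoms deteriorate after 2 or more missed PRO assessment visits or the patient dies after 2 or more missed PRO assessment visits". The consequence is that "the patient will be censored at the time of the last PRO assessment where the symptom could be evaluated".

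The next subsection, on HRQoL/function, uses the same trigger and ends "the patient will be censored at the time of the last PRO assessment where HRQoL/function could be evaluated".

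For PFS, section 9.4.1.1 handles progression or death after two or more consecutive missed visits differently: "the patient will be censored at the time of the latest evaluable RECIST 1.1 assessment prior to the 2 missed visits".

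On treatment, Table 1 schedules the EORTC QLQ-C30 "q4w (±7 days relative to Cycle 1 Dose 1 date) until treatment discontinuation". After follow-up Month 3, Table 2 has patients without PD who "will continue with q8w (±7 days relative to follow-up Month 3 visit date) until PD".

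The derived times feed the analysis in section 9.4.2.7: "These analyses will be performed for the FAS using a log-rank test stratified by the same covariates as for the primary PFS endpoint". Kaplan-Meier plots and medians accompany the test. The scales analysed include those named in the secondary objectives: global health status/QoL, physical function, fatigue and pain.

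**The concern.** A missed-visit rule exists because, when an event is first seen after a long gap, nobody knows when in the gap it happened. The usual remedy is to stop follow-up at the last assessment before the gap. The PFS rule says this. The two PRO rules lack the words that point back before the gap.

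The deterioration limb fires only when a questionnaire was completed and scored after the gap. That questionnaire is evaluable, so the last evaluable assessment cannot be earlier than the observed deterioration. It is later still if the patient goes on completing questionnaires. A patient known to have deteriorated would stay in the risk set as event-free through the unobserved gap, and possibly beyond the deterioration. Kaplan-Meier and log-rank methods treat time up to censoring as event-free, which here contradicts the patient's own data.

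**Working it through.** The protocol states no figure that depends on this rule, so there is nothing to reproduce. The check has three parts.

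**1. The wording side by side**

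| Endpoint | Trigger | Censoring date | Limited to before the gap? |
|---|---|---|---|
| PFS (9.4.1.1) | progression or death after 2 or more missed visits | latest evaluable RECIST 1.1 assessment | yes |
| Symptoms (9.4.1.3) | deterioration or death after 2 or more missed PRO visits | last evaluable PRO assessment | no |
| HRQoL/function (9.4.1.3) | same | last evaluable PRO assessment | no |

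In the symptom subsection, the sentence just before the rule uses almost the same phrase for living patients with no deterioration. There it plainly means the last assessment in the record. A programmer who reads the phrase consistently would apply that date to the deteriorated patient too.

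**2. Dates on the protocol's own schedule**

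Let q be the visit interval, with the last evaluable visit before the gap at 2q, visits 3q and 4q missed, and deterioration seen at 5q.

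- Pre-gap rule: censor at 2q.
- Literal rule: censor at 5q, or at 6q if one more evaluable visit follows.
- Extra event-free time: 5q − 2q = 3q, or 6q − 2q = 4q.

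| Schedule | Pre-gap | Literal | Literal, one later visit | Extra time |
|---|---|---|---|---|
| q = 28 days | Day 56 | Day 140 | Day 168 | 84 to 112 days |
| q = 56 days | Day 112 | Day 280 | Day 336 | 168 to 224 days |

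The minimum is three intervals: 84 / 7 = 12 weeks, or 168 / 7 = 24 weeks. These are nominal because each visit has a window of ±7 days.

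**3. Effect on the analysis (illustrative)**

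All inputs are assumptions, since the protocol gives none: 6,000 simulated patients per scenario, exponential deterioration with median 4 months, 26 four-weekly visits, and 10%, 20% or 40% of patients with one two-visit gap starting at one of the first ten visits. Dropout and death are not modelled. The literal rule is taken at its mildest, with censoring at the deteriorating visit. The rate is events divided by total follow-up, per month.

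| Patients with a gap | Patients under the rule | Rate, pre-gap rule | Rate, literal rule | Relative drop | KM median, both rules |
|---|---|---|---|---|---|
| 10% | 2.0% | 0.1582 | 0.1568 | 0.0014 / 0.1582 = 0.9% | 140 days |
| 20% | 3.7% | 0.1563 | 0.1537 | 0.0026 / 0.1563 = 1.7% | 140 days |
| 40% | 8.3% | 0.1506 | 0.1451 | 0.0055 / 0.1506 = 3.7% | 140 days |

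With no gaps the rate is 0.1606, so the pre-gap rule itself lowers it: at 10% with a gap, by 0.1606 − 0.1582 = 0.0024, against a further 0.0014 from the literal wording. Censoring later than the deteriorating visit would widen the second part.

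For 150 randomized patients, 2.0% is 150 × 0.020 = 3 patients and 8.3% is 150 × 0.083 ≈ 12, across both arms and before the baseline-score exclusions in section 9.4.1.3.

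**The case against.** The best defence is that this is loose drafting with an obvious intention. One censoring date serves two triggers. For the death trigger the last evaluable PRO assessment necessarily precedes the gap, and reading the deterioration trigger the same way gives the PFS rule. That is probably what was meant. It bears on severity, but it does not cure the text: the protocol writes the rule out in full, and nothing elsewhere supplies the missing limit. Section 9.4 leaves missing-data procedures to the SAP and section 9.4.1.3 promises more QLQ-C30 detail there, but this rule is stated, not deferred. A SAP that copies it inherits the fault, and one that corrects it departs from the protocol.

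Four stronger readings are tempting and are not supported:

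- **That the omission loses the event.** The corrected rule also censors without an event, by design. Only the time in the risk set differs.
- **That median time to deterioration is distorted.** The median stayed at 140 days in every scenario.
- **That each affected patient gains a particular, much longer average time.** Any average beyond the three-interval minimum depends on assumed numbers of visits, missingness and dropout.
- **That one arm is favoured.** This would need missed questionnaires to differ by arm. The trial is double-blind, the protocol gives no reason to expect a difference, and no between-arm effect has been calculated.

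It also stands that the PRO endpoints lie outside the PFS-then-OS testing sequence in sections 9.1 and 9.4.10. No alpha, power or success criterion depends on this rule.

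**Conclusion.** Wrong as written, minor. For patients who deteriorate after two or more missed PRO visits, both rules in section 9.4.1.3 literally give a censoring date at or after the observed deterioration. They therefore count at least three visit intervals (nominally 12 weeks at 4-weekly visits, 24 weeks at 8-weekly visits) as deterioration-free. That minimum follows from the wording and the schedule alone.

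The wider effect rests on assumptions and is probably small: about 2% to 8% of patients under the rule, an event rate about 1% to 4% lower, and an unchanged median, if 10% to 40% of patients have a two-visit gap. It would matter more if such gaps were commoner, or if patients kept completing questionnaires well after deteriorating. Deaths after a gap are handled correctly. PFS, OS, sample size and alpha are untouched.

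**What to change.** In both subsections of section 9.4.1.3 (symptoms and HRQoL/function), state that the patient is censored at the last PRO assessment before the two or more missed visits at which the symptom, or HRQoL/function, could be evaluated. This matches the PFS rule in section 9.4.1.1. Carry the same wording into the SAP and the programming specification for these endpoints.

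The cost is one phrase in two paragraphs. No data collection, visit schedule or sample size changes.

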## 9.2 Sample size determination

The study is sized to characterize the PFS benefit of durvalumab in combination with olaparib versus durvalumab monotherapy in first-line patients with unresectable Stage IV UC.

Approximately 150 patients globally will be randomized in a 1:1 ratio to either the durvalumab + olaparib treatment group or the durvalumab + placebo treatment group, 75 patients per arm. The randomization will be stratified based on HRR status (mutant versus wild type) and Bajorin risk index (0 versus 1 versus 2).

The DCO for the primary analysis of PFS will occur when approximately 118 PFS events have occurred across both treatment groups (79% maturity). Assuming a median survival of 3 months for durvalumab monotherapy and recruitment of 150 patients in 6 months, it is estimated that this DCO will occur 7 months following recruitment of the last patient.

If the true PFS hazard ratio (HR) is 0.55 (likely to correspond to an 82% prolongation of PFS), the study will have 90% power to demonstrate a statistically significant difference for PFS at the 2-sided 5% significance level.

The smallest treatment difference that could be statistically significant at the primary analysis of PFS is an HR of 0.69 (assuming a 2-sided p-value of 0.5).

There will be up to 2 analysis timepoints for OS. The first OS analysis will occur at the same time as the primary PFS analysis and will be based on an estimated 44 OS events across therapies (29% maturity), and the second OS analysis will occur when

approximately 100 OS events have occurred (67% maturity). With an approximate 6-month recruitment period and an assumed median OS of 16 months in the durvalumab + placebo arm, it is anticipated that the final analysis will be performed at approximately 27 months after the last patient has been recruited.

Assuming the true OS HR is 0.75, the study will have 30% power to demonstrate a statistically significant OS effect with a 5% 2-sided significance level, allowing for 2 analyses of the data. The smallest treatment difference at the second analysis of OS that could be statistically significant is an HR of 0.68.

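### Time to PRO deterioration counts death as an event, yet censors at Day 0 a patient who dies within two PRO visits of baseline without a post-baseline form

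*Protocol*

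**What the plan says.** Section 9.4.1.3, Time to symptom deterioration, makes the event a clinically meaningful worsening "or death (by any cause) in the absence of a clinically meaningful symptom deterioration". A death is included "only if the death occurs within 2 visits of the last PRO assessment where the symptom change could be evaluated". The paragraph on censoring ends: "If a patient has no evaluable visits or does not have baseline data they will be censored at Day 0". The HRQoL/function definition that follows has the same structure: the same composite event, the same restriction on deaths and the same Day 0 sentence.

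The analysis population is already limited by baseline score: "The population for the analysis of time to symptom deterioration will include a subset of the FAS who have baseline scores of" 90 or less for symptoms, and 10 or more for HRQoL/function.

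Table 1 schedules the questionnaire at Cycle 1 and then "q4w (±7 days relative to Cycle 1 Dose 1 date) until treatment discontinuation". Section 9.4.2.7 gives the test: "These analyses will be performed for the FAS using a log-rank test stratified by the same covariates" as for PFS.

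For PFS, Section 9.4.1.1 says that patients with no evaluable visits or no baseline data follow a different rule: "they will be censored at Day 1 unless they die within 2 visits of baseline; then they will be treated as an event", dated at death.

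**The concern.** The endpoint counts death as a bad outcome, but the derivation removes some of the earliest deaths. Consider two patients. One completes the baseline form and dies in week 3. The other completes the week-4 form without worsening and dies in week 7. Each died three weeks after the last form. The second is an event, while the first is censored at time zero.

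For the first patient the censoring is caused by the death itself, so it is informative. Deterioration-free curves start too high in both arms. If one arm had more early deaths, from toxicity or rapid progression, part of that difference would leave the comparison. Global health status/QoL, physical function, fatigue and pain are named secondary PRO measures, and all four use this rule.

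**Working it through.** The protocol states no event count or power for the PRO endpoints, so there is no figure to reproduce. The check has a logical part and a size part.

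**Applying the rule** to a patient with a baseline score who dies in week 3 with no further form:

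1. The patient has a qualifying baseline score and is in the population.
2. The death clause needs an assessment where the change could be evaluated. A baseline form alone gives no change, so the death is not counted.
3. There is no post-baseline form, so there is no evaluable visit, and the Day 0 sentence applies. It has no exception for death.
4. Under the PFS rule, a patient with no evaluable visit who dies within two visits of baseline is an event at the date of death.

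Patients without baseline data are already outside the population. Within it, the Day 0 sentence therefore acts on patients who have a baseline form and nothing after it.

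**Number of patients.** Inputs from Section 9.2: "75 patients per arm", control median OS 16 months, OS HR 0.75. Assumption: exponential survival from randomisation, with 4.348 weeks per month. The probability of death by week w is 1 − exp(−ln2 × HR × w / (16 × 4.348)), with HR = 1 for control. Multiplied by 75:

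| Week | Control | Combination | Total of 150 |
|---|---|---|---|
| 3 | 2.2 | 1.7 | 3.9 |
| 4 | 2.9 | 2.2 | 5.1 |
| 5 | 3.6 | 2.8 | 6.4 |
| 8 | 5.8 | 4.4 | 10.1 |

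The first post-baseline form is due at week 4, so about 5 patients die before it. The ±7-day window gives 3.9 to 6.4. If, as a further assumption, 30% of those dying in weeks 4 to 8 also lack the week-4 form, the count is 5.1 + 0.3 × (10.1 − 5.1) = 6.6. The week-8 total of 10.1 is reached only if every patient who dies by then lacks a post-baseline form.

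**Effect on the curve (control arm).** Assume that worsening is exponential with median m months and is seen at 4-weekly visits. Eight weeks is 8 / 4.348 = 1.84 months. With deaths counted, the 8-week deterioration-free proportion is S = exp(−ln2 × 1.84 / m) × exp(−ln2 × 1.84 / 16). Removing the 3.9% who die before week 4 at time zero gives S / (1 − 0.039).

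| Assumed m | Deaths counted | Day 0 rule | Difference |
|---|---|---|---|
| 2 months | 0.488 | 0.508 | 2.0 points |
| 3 months | 0.604 | 0.628 | 2.5 points |
| 4 months | 0.671 | 0.699 | 2.7 points |

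**Effect on the HR.** In a simulation (600 trials, 75 per arm, the protocol's OS assumptions, m = 4 months in both arms, 30% of patients dying in weeks 4 to 8 lacking the week-4 form, 12 months of follow-up), the rule as written moves the HR by about 0.01 towards 1. The standard error of the log HR is about 0.17.

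**The case against.** **The wording leaves some room.** The death clause speaks of evaluating the symptom change, while the censoring sentences speak of evaluating the symptom, which a baseline form would satisfy. Baseline could then be read as an evaluable visit. This is the weaker reading: the Day 0 sentence names missing baseline data separately, and the death clause still requires an evaluable change. It does show that the text needs clarifying.

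**The restriction may be deliberate.** A PRO endpoint may count only deaths close to an informative assessment, and PFS is a different endpoint, so a different rule is not in itself a contradiction. But the protocol counts a death three weeks after a week-4 form and discards one three weeks after the baseline form, and gives no reason.

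**The consequence is limited.** This stands. Only PFS and then OS carry alpha (Sections 9.1 and 9.4.10). Time to deterioration is one of several QLQ-C30 analyses, alongside improvement rates and mean change. Early deaths still count in OS and, within two visits of baseline, in PFS, so an imbalance would be visible there.

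**Two stronger readings are tempting.** A reader might infer that everyone who dies before a post-baseline form is wrongly dropped. The documents do not support that: a death after two or more missed PRO visits is censored anyway by the separate missed-visit rule. A reader might also infer a material bias in the treatment comparison. That needs a marked excess of early deaths in one arm, which the protocol does not assume; its own OS figures put slightly more early deaths in control (2.9 against 2.2 by week 4).

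**Conclusion.** The point holds for deaths within two PRO visits of baseline with no post-baseline form. It is a rule that the protocol fixes, not a detail left to the SAP: a SAP that follows it inherits the defect, and one that corrects it departs from the protocol.

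About 5 of 150 patients are affected, roughly 4 to 7, with about 10 as an upper bound. This rests on the protocol's OS median and HR and on exponential survival. The count may be lower, because inclusion criterion 10 requires a life expectancy of at least 12 weeks. The 8-week deterioration-free proportion is too high by 2 to 3 percentage points in the control-arm illustration, whose deterioration medians are assumed. The combination arm is affected in the same direction. The effect on the HR is small unless early mortality differs between arms, and then the rule partly hides that difference. PFS, OS and alpha control are unaffected. The correction is worth making because it is simple and brings the derivation into line with the endpoint's own definition.

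**What to change.** Amend two sentences in each of the two time-to-deterioration definitions in Section 9.4.1.3, and carry the change into the SAP derivation.

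1. **Death clause.** Keep the present condition and add an alternative: a death also counts if it falls within 2 PRO visits of baseline and there is no evaluable post-baseline assessment. Without this edit the existing only-if condition would contradict the second change.
2. **Day 0 sentence.** Replace it with: *Patients with baseline data but no evaluable post-baseline visit will be censored at Day 1, unless they die within 2 PRO visits of baseline, in which case they are an event at the date of death.* Day 1 matches the PFS convention in Section 9.4.1.1.

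The cost is two sentences in each of two paragraphs and a few more events. Death dates are already collected, so no new data are needed.
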